2.1.2 Secondary Efficacy Objectives

A secondary efficacy objective for this study is to evaluate the efficacy of RO7198457 plus pembrolizumab compared with pembrolizumab alone on the basis of the following endpoints:

- Objective response rate (ORR), defined as the proportion of patients with a complete response (CR) or partial response (PR) on two consecutive occasions ≥ 4 weeks apart, as determined by the investigator according to RECIST v1.1
- OS after randomization, defined as the time from randomization to death from any cause
- Duration of response (DOR), defined as the time from the first occurrence of a documented objective response to disease progression or death from any cause, as determined by the investigator according to RECIST v1.1
- Mean change from baseline in health-related quality of life (HRQoL) scores as assessed through use of the two-item global health status (GHS)/HRQoL subscale (Questions 29 and 30) of the European Organisation for Research and Treatment of Cancer Quality of Life—Core 30 (EORTC QLQ-C30) at specified timepoints

Another secondary objective is to evaluate the efficacy of RO7198457 plus pembrolizumab in patients who have progressed following pembrolizumab monotherapy on the basis of the following endpoint:

- ORR, defined as the proportion of patients with a CR or PR on two consecutive occasions \geq 4 weeks apart, as determined by the investigator according to RECIST v1.1, at the time of crossover

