3.1.5 Internal Monitoring Committee Reviews

The primary responsibility of the IMC is to review the available safety data and make recommendations on study conduct to ensure enhanced patient safety while patients receive study treatment. The IMC will periodically evaluate the accumulating safety data from all patients treated in this study. Following analysis of the primary endpoint of PFS, expected to occur approximately 24 months after enrollment of the first randomized patient, future safety analyses will be conducted. The IMC Chair will be a medical oncologist who is not the Medical Monitor and is not associated with the study. Other IMC members may include, but are not limited to, a safety scientist, biostatistician, and clinical pharmacologist. The IMC will operate according to a pre-specified charter and make recommendations on study conduct related to patient safety (see Section 5).

The IMC will review the safety data during the safety run-in stage as described in Section 3.1.2. During the randomization stage, safety data from the first 20 patients in Arm B treated with at least 1 cycle of RO7198457 plus pembrolizumab will be formally reviewed by an IMC. Following the initial data reviews in the safety run-in and randomization stages, the IMC will review the safety data approximately every 6 months, or more frequently if recommended by the IMC Chair or the Medical Monitor. The safety data may include, but are not limited to, demographic data, adverse event data (including serious adverse events and adverse events of special interest), study conduct data, and relevant laboratory data.

In addition, the Medical Monitor may request additional safety reports and may call for ad-hoc meetings of the IMC at any time during the study to review ongoing safety data for a benefit-risk balance.

The IMC may make recommendations regarding study conduct, including, but not limited to, the following: continuing the study as per the protocol, performing additional safety analyses, amending the study protocol, holding patient enrollment pending further safety evaluations, holding/discontinuing study treatment, or terminating the study.

The IMC may share preliminary results from these safety and interim analyses with appropriate Sponsor employees and with the investigators, as the IMC Chair deems necessary.

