4.1.3.1 Inclusion Criteria for Crossover Treatment

- Confirmed progression of disease as assessed by investigator per RECIST v1.1 after at least one dose of pembrolizumab in Arm A

Disease progression must be confirmed by a consecutive assessment ≥ 4 weeks from the date first documented.

Patients who complete 24 months of pembrolizumab and experience disease progression < 6 months after discontinuing pembrolizumab may also be eligible to cross over.
- ECOG Performance Status of 0 or 1 (see [Appendix 6](#))
- For women of childbearing potential: agreement to remain abstinent (refrain from heterosexual intercourse) or use contraceptive measures, and agreement to refrain from donating eggs, as defined below:

Women must remain abstinent or use contraceptive methods that result in a failure rate of $< 1\%$ per year during the treatment period and for at least 90 days

after the final dose of RO7198457 and at least 4 months after the final dose of pembrolizumab, whichever occurs later. Women must refrain from donating eggs during this same period.

A woman is considered to be of childbearing potential if she is postmenarcheal, has not reached a postmenopausal state (≥ 12 continuous months of amenorrhea with no identified cause other than menopause), and is not permanently infertile due to surgery (i.e., removal of ovaries, fallopian tubes, and/or uterus) or another cause as determined by the investigator (e.g., Müllerian agenesis). The definition of childbearing potential may be adapted for alignment with local guidelines or requirements.

Examples of contraceptive methods with a failure rate of $< 1\%$ per year include bilateral tubal ligation, male sterilization, and established proper use of hormonal contraceptives that inhibit ovulation, hormone-releasing intrauterine devices, and copper intrauterine devices.

Hormonal contraceptive methods must be supplemented by a barrier method plus spermicide.

The reliability of sexual abstinence should be evaluated in relation to the duration of the clinical trial and the preferred and usual lifestyle of the patient. Periodic abstinence (e.g., calendar, ovulation, symptothermal, or postovulation methods) and withdrawal are not acceptable methods of contraception.

If required per local guidelines or regulations, locally recognized acceptable methods of contraception and information about the reliability of abstinence will be described in the local Informed Consent Form.

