6.1 DETERMINATION OF SAMPLE SIZE

The purpose of this study is estimation and hypothesis generation regarding the safety and efficacy of RO7198457 plus pembrolizumab relative to pembrolizumab monotherapy.

Enrollment of 120 randomized patients (approximately 80 patients in the RO7198457 plus pembrolizumab arm and 40 patients in the standard-of-care arm) is expected to occur 18 months after first patient in (FPI).

The null and alternative hypotheses with respect to PFS can be phrased in terms of the survival function $S_{PFS_a}(t)$ in Arm A (control) and $S_{PFS_b}(t)$ in Arm B (experimental):

$$H_0: S_{PFS_a}(t) = S_{PFS_b}(t) \text{ vs. } H_a: S_{PFS_a}(t) \neq S_{PFS_b}(t)$$

in our PFS primary efficacy endpoint, the first efficacy endpoint tested in a hierarchical fashion. However, the totality of data, including safety and sensitivity analyses while accounting for non-proportional hazards as stated in Section 6.4.1 will be important for evaluating clinical benefit.

Point and interval estimates for the primary endpoint of PFS HR and key secondary endpoint of improvement in ORR (i.e., Δ ORR) in the RO7198457 plus pembrolizumab arm relative to the pembrolizumab arm will be obtained.

To control for Type 1 error, two pre-specified interim analyses and one primary analysis will be conducted with a Haybittle-Peto alpha spending approach (Haybittle 1971; Peto et al. 1976). Testing will be performed in a hierarchical fashion testing PFS followed by secondary endpoints. Each interim analysis will be conducted at the two-sided significance level of 0.001. The final analysis will be conducted at the two-sided significance level of 5%. If PFS is significant at the two-sided significance level of 5%, alpha will be passed down to the secondary endpoints in order of presentation below.

The study will not, however, have adequate power to detect other potentially clinically meaningful differences in PFS and Δ ORR.

improvement in ORR in the RO7198457 plus pembrolizumab arm relative to the pembrolizumab arm (assuming a 33% ORR in the pembrolizumab arm). Thus, a statistically negative outcome does not rule out a potentially clinically meaningful outcome.

[Table 11](#) and [Table 12](#) show the power and CIs for several possible true underlying improvements in PFS and ORR in favor of the RO7198457 plus pembrolizumab arm. The study will not have adequate power to detect other potentially clinically meaningful differences in PFS or ORR. See [Table 11](#) below.

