6.4.1 Primary Efficacy Endpoint of PFS

PFS is defined as the time from randomization to the date of first documented disease progression or death, whichever occurs first. Disease progression for PFS analysis will be determined on the basis of investigator assessment using RECIST v1.1. The primary PFS analysis will occur after approximately 80 events have been observed in the primary population or approximately 24 months from FPI.

Data for a patient without disease progression or death as of the clinical data cutoff date will be censored at the time of the last tumor assessment (or at the date of randomization plus 1 day if no tumor assessment was performed after the baseline visit). Data from a patient who is lost to follow-up will be included in the analysis and censored on the last date of tumor assessment that the patient was known to be progression free.

Kaplan-Meier methodology will be used to estimate the PFS curve and median PFS for each treatment arm. A stratified Cox proportional-hazards model will be used to estimate the HR and its 95% CI. The two-sided stratified log-rank test will be used to compare PFS between the two treatment arms at the two-sided significance level of 5%. Unstratified modeling approaches may be used to assess the robustness of the PFS primary endpoint results. To account for patients who may discontinue study treatment prior to first administration of RO7198457, a landmark analysis restricted to patients treated at Cycle 2 and beyond may be performed with PFS time calculated starting from Cycle 2, Day 1 on the ITT and modified subsets.

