6.4.2 Secondary Efficacy Endpoints

ORR Analysis

ORR is defined as the proportion of patients who have experienced a CR or PR on two consecutive occasions \geq 4 weeks apart, as determined by the investigator according to RECIST v1.1. Objective response will be evaluated by treatment arm. Patients without postbaseline overall response assessments will be counted as non-responders. An estimate of the difference between the ORR in the two arms will be computed along with its 95% CI. The Mantel-Haenszel test will be used to compare the ORR between the two treatment arms at the two-sided significance level of 5%, if PFS analysis is significant at the 5% threshold for type I error control, stratified by the protocol-defined stratification factors. Final ORR analysis will occur at the time of primary PFS analysis.

OS Analysis

OS is defined as the time from randomization to death from any cause. Data for patients who are alive at the time of the analysis data cutoff will be censored at the last date they were known to be alive. Data from patients without postbaseline information will be censored at the date of randomization plus 1 day. A final OS analysis will be performed at approximately 40% event maturity at approximately 40 months. Statistical analyses will be performed similarly to PFS as described in [6.4.1](#).

Duration of Response Analysis

DOR is defined as the time from the first occurrence of a documented objective response to disease progression or death from any cause, whichever occurs first, as determined by the investigator according to RECIST v1.1. The analysis of DOR will include only patients who achieved an objective response to study treatment. DOR will be estimated using the Kaplan-Meier methodology.

Crossover Analysis

The statistical analysis to evaluate the efficacy of patients who have progressed following pembrolizumab monotherapy and received the combination of RO7198457 plus pembrolizumab as assessed by ORR per RECIST v1.1 will be performed as described in Section 6.4.2.

Patient-Reported Outcomes Analysis

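### The crossover ORR has no data cutoff of its own, and the one it appears to inherit, the primary PFS analysis, is too early for a response measured after crossover

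*Combined protocol and SAP*

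**What the plan says.** Section 2.1.2 sets the objective: "Another secondary objective is to evaluate the efficacy of RO7198457 plus pembrolizumab in patients who have progressed following pembrolizumab monotherapy". ORR is the only endpoint listed for it.

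For the analysis, the Crossover Analysis paragraph of Section 6.4.2 states that efficacy "as assessed by ORR per RECIST v1.1 will be performed as described in Section 6.4.2", which is a reference to itself. The ORR rules in that section include two that matter here:

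- Timing: "Final ORR analysis will occur at the time of primary PFS analysis".
- Missing assessments: "Patients without postbaseline overall response assessments will be counted as non-responders".

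Section 6.4.1 dates the cut: "The primary PFS analysis will occur after approximately 80 events have been observed in the primary population or approximately 24 months from FPI". Section 3.1.5 describes the same analysis as "expected to occur approximately 24 months after enrollment of the first randomized patient". Section 6.1 expects the 120 randomised patients to be enrolled over 18 months. Section 6.4.2 also plans a final OS analysis at about 40 months.

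No visible text gives the crossover ORR a separate cutoff, a minimum follow-up or a denominator. Section 4.1.3.1 also opens a second, late route: "Patients who complete 24 months of pembrolizumab and experience disease progression < 6 months after discontinuing pembrolizumab may also be eligible to cross over".

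**The concern.** The clock for this endpoint starts much later than randomisation. An Arm A patient must be randomised, progress, have progression confirmed at least 4 weeks later (Section 4.1.3.1), stay on pembrolizumab until vaccine is available (Appendix 2, footnote a), start crossover, and then respond on two occasions at least 4 weeks apart. With accrual to month 18 and a month-24 cut, every randomised patient has at least 6 months for the main ORR. A crossover patient may have days.

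A patient who has just crossed over cannot yet meet the confirmed-response definition, but would enter the rate as a failure. Patients slow to progress on pembrolizumab may not have crossed over at all. Both effects come from calendar time rather than from treatment. They would affect the only figure that answers a stated secondary objective.

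**Working it through.** **Consistency of the plan's cut.** The plan pairs 80 events with 24 months. The hazard ratios in Table 11 are redacted, so this cannot be strictly reproduced. With uniform 18-month accrual, 80:40 allocation, exponential PFS, a 5.5-month control median (Section 3.3.6 gives 5-6 months) and no dropout, expected events at month 24 are:

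| Assumed HR | Continuous time | Read at scheduled scans |
|---|---|---|
| 0.5 | 79.7 | 76.4 |
| 0.6 | 84.8 | 81.4 |

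The pairing is therefore coherent for an HR of about 0.5-0.6, and month 24 is a fair reference cut.

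**Time needed after crossover.** Appendix 2 puts the first scan at Week 12 and the next at Week 18. A response confirmed at least 4 weeks later needs 12 + 4 = 16 weeks at the earliest, or 12 + 6 = 18 weeks on scheduled scans.

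**Hand check** (1 month = 4.348 weeks). A patient randomised at month 18 has 6 × 4.348 = 26.1 weeks to the cut. With progression at Week 12, confirmation 4 weeks later and no wait, crossover starts at Week 16. That leaves 26.1 − 16 = 10.1 weeks, short even of the first post-crossover scan.

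To have 18 weeks, the fastest progressor must be randomised by:

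- Shortest delays: 24 − (12 + 4 + 0 + 18)/4.348 = 24 − 7.8 = month 16.2.
- Longest delays modelled: 24 − (12 + 6 + 6 + 18)/4.348 = 24 − 9.7 = month 14.3.

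**Share affected.** Crossover start = entry + time of the scan showing progression + confirmation + wait. Inputs: entry uniform over 0-18 months; exponential PFS, median 5 or 6 months; progression read at protocol scans; confirmation 4 or 6 weeks; wait 0 or 6 weeks (assumed). I simulated 400,000 Arm A patients per scenario, taking progression by about Week 130 as crossover-eligible:

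| Cut | Eligible patients who have started crossover | Starters with <16 weeks | <18 weeks | <12 weeks |
|---|---|---|---|---|
| Month 24 | 71-81% | 18-25% | 21-28% | 12-19% |
| Month 40 | 98-99% | 1-3% | 2-3% | 1-2% |

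**Wider assumptions at month 24** (continuous or scan-read progression, wait up to 12 weeks, 16-18 weeks needed): 15-31% with uniform accrual and 22-48% with linearly rising accrual, so 15-48% overall. A mid case is 28% (uniform, median 5.5 months, scheduled scans, 6-week confirmation, 6-week wait, 18 weeks needed). The same case leaves about 3% at month 40. Over these assumptions the share is 27-60% for a cut at month 20, 11-41% at month 26 and 5-20% at month 30.

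**Effect on the rate.** If all 18-28% count as non-responders, the ORR is multiplied by 1 − 0.28 = 0.72 to 1 − 0.18 = 0.82. An assumed true 20% would read about 14-16%.

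**Completed-24-months route, first randomised patient.** The first scheduled scan after the course is Week 108 (24.8 months). Confirmation is then Week 112 (25.8 months) and the earliest confirmed response is Week 112 + 16 = 128 (29.4 months). The fastest conceivable path counts from Cycle 34 Day 1 (34 cycles of 3 weeks, so Week 99, 22.8 months). An immediate unscheduled scan and 4-week confirmation give Week 103 (23.7 months) before any wait, and a confirmed response at Week 119 (27.4 months). Both fall after month 24.

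**The case against.** **The cut is inferred.** The cross-reference can be read as method only. The timing sentence closes a paragraph about a two-arm comparison, with a difference in ORR, a Mantel-Haenszel test and gating on PFS, most of which cannot apply to a single group. This stands. A reader might infer that the plan fixes the crossover ORR at the primary PFS analysis, but the text supports only a literal reading. The alternative is that no cutoff is stated, which needs the same repair.

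**The size depends on assumptions.** Accrual shape is not given and the crossover start limit is redacted. Section 4.5.5 sends crossover scans to Appendix 2, footnote k, which counts weeks from Cycle 1 Day 1 of pembrolizumab. If the original clock keeps running at 6-week intervals, 12 weeks suffice and the share is 12-19%. Section 4.5.5 also allows unscheduled scans, so the shortfall applies to scheduled scans and is not absolute. Section 1.4 expects PFS plateaus. With an assumed 15-35% plateau and the same medians, 16-27% fall below 18 weeks and 8-18% below 12 weeks. Plateaus also slow events, so an event-driven cut could come later. All of this widens the range, and rising accrual widens it upward. None of it removes the shortfall at month 24.

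**The practical effect is limited.** Arm A has about 40 patients, crossover is optional, and no crossover hypothesis is stated. If 20 crossed over (assumed), 20% against 15% is 4 responders against 3, with exact 95% intervals of 6-44% and 3-38%. That is fair as to precision, but the bias runs in one direction and costs little to avoid.

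**Conclusion.** The plan gives the crossover ORR no cutoff of its own, and the only one it could inherit is too early. At month 24 about 18-28% of crossed-over patients have had less than the 16-18 weeks needed on scheduled scans, against about 2-3% at month 40. This rests on uniform 18-month accrual, exponential PFS with a 5-6 month median, 4-6 weeks to confirm progression and a 0-6 week wait. The share is 12-19% if 12 weeks suffice and about 15-48% under wider accrual and delay assumptions. The multiplier of 0.72-0.82 is a worst case in which every such patient counts as a failure.

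Two stronger readings are not supported. A reader might take a share as high as 37% as the month-24 result under these base assumptions. That end comes from cuts at months 20-22, which at these medians correspond to an HR of about 0.8-1.0, and the planned HR is redacted. A reader might also conclude that crossover after completing 24 months of pembrolizumab cannot occur at all before the analysis. The cut may be event-driven and later, and 34 cycles put the last dose at 22.8 months, so a first crossover near month 24 is just conceivable. What holds is that this route cannot contribute a confirmed response at a 24-month cut.

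The primary PFS analysis is unaffected. A stated secondary objective is.

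**What to change.** Replace the bare cross-reference in the Crossover Analysis paragraph of Section 6.4.2 with wording such as:

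> The final crossover ORR will be analysed at the final OS cutoff (approximately 40 months) in all Arm A patients whose first crossover dose of RO7198457 was at least 18 weeks before the cutoff, whether or not they were scanned. Patients without a post-crossover assessment count as non-responders. Any crossover ORR reported at the primary PFS analysis is preliminary and uses the same 18-week rule.

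Exempt this endpoint from the sentence that places the final ORR at the primary PFS analysis. Setting the denominator by time since first crossover dose, and not by having been scanned, removes patients who are merely too recent while keeping early failures in.

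The cost is a few sentences. No extra patients or scans are needed, because crossover assessments and the OS analysis are already planned. The downside is that the final crossover ORR is reported later, with the OS analysis.

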6.4.3 Exploratory Efficacy Endpoints

A 12-month PFS rate will be analyzed in the ITT. The PFS rate will be estimated using Kaplan Meier methodology for each treatment arm, along with 95% CIs calculated using the standard error derived from the Greenwood formula. The 95% CI for the difference in the PFS rate between the two treatment arms will be estimated using the normal approximation method.

PFS, ORR, and DOR may be further evaluated using definitions of response per iRECIST criteria (see [Appendix 5](#)) in all randomized patients.

Exploratory PRO endpoints may be evaluated to further characterize the patient experience when treated with RO7198457 plus pembrolizumab versus pembrolizumab alone. PRO scales (EORTC scales, PRO-CTCAE scale, single-item bother, and WPAI) completion, compliance rates, and reasons for missing data will be summarized at each timepoint by treatment arm for each measure in the ITT population. Summary statistics at each timepoint including proportion of patients with meaningful changes, time-to-event analyses, and longitudinal analyses as relevant will be generated to inform patients' experience in each treatment arm.

6.5 SAFETY ANALYSES

Safety analyses will be conducted in all randomized patients who received at least one dose of RO7198457 and/or pembrolizumab. Safety analyses will be performed by treatment arm and will be based on actual treatment received. Specifically, a patient will be included in the RO7198457 plus pembrolizumab arm in the safety analyses if the patient receives any amount of RO7198457, regardless of the initial treatment assignment at randomization.

Safety endpoints will include incidence and severity of adverse events (using NCI CTCAE v5.0), including serious adverse events and adverse events of special

interest, changes from baseline in clinically relevant vital signs, physical findings, and clinical laboratory results following the administration of RO7198457 plus pembrolizumab or solely pembrolizumab. Drug exposure will be summarized, including duration, dosage, and dose intensity. Verbatim description of adverse events will be mapped to the MedDRA thesaurus terms and graded according to the NCI CTCAE v5.0.

All adverse events that occur during or after the first study treatment, until 90 days after the final dose of study drug or initiation of another systemic anti-cancer therapy, whichever occurs first, will be summarized by treatment arm and NCI CTCAE grade. In addition, serious adverse events and adverse events leading to study treatment discontinuation or interruption will be summarized accordingly. Multiple occurrence of the same event will be counted once at the maximum severity. Laboratory data with values outside of the normal ranges will be identified. Additionally, selected laboratory data will be summarized by treatment arm and grade. Vital signs will also be summarized by treatment arm and visit. Deaths and causes of deaths will be summarized. Analyses of safety endpoints will be conducted at the time of the primary efficacy analysis.

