3. STUDY DESIGN

3.1 DESCRIPTION OF THE STUDY

3.1.1 Overview of Study Design

This is a Phase II, randomized, open-label, multicenter study designed to evaluate the efficacy and safety of RO7198457 plus pembrolizumab compared with pembrolizumab alone in patients with previously untreated advanced melanoma. The patient population includes patients with unresectable locally advanced (Stages IIIC and IIID) and metastatic (recurrent or de novo Stage IV) melanoma. This study will be conducted globally.

The study consists of two stages: an initial safety run-in stage and a randomized stage. Each stage will have a two-part screening period (Part A and Part B), a treatment period, and post-treatment follow-up period.

The safety run-in stage will consist of a single arm that will enroll approximately 6–12 patients. Patients in the safety run-in will receive at least 1 cycle (21 days) of 200 mg pembrolizumab monotherapy administered by IV infusion. Once RO7198457 is manufactured and available, patients will receive 200 mg pembrolizumab IV every 3 weeks (Q3W) and [REDACTED] RO7198457 IV as detailed in Section 4.3.2.1. Accrual in the randomized stage will not start until an Internal Monitoring Committee (IMC) has reviewed the safety data of the first 6 patients treated in the safety run-in stage (see Section 3.1.2).

The randomized stage will enroll approximately 120 patients, randomized in a 2:1 ratio, to either the experimental or control arm:

[figure not shown]
- Arm A (control): 200 mg pembrolizumab administered by IV infusion Q3W
- Arm B (experimental): at least 1 cycle of 200 mg pembrolizumab administered by IV infusion followed by 200 mg pembrolizumab IV Q3W and [REDACTED] RO7198457 IV as detailed in Section 4.3.2.1.

A third arm (Arm C) may be added to the study at a later time via a protocol amendment, pending the results of dose escalation in an ongoing Genentech sponsored Phase Ib study (GO39733). Patients in this arm would receive RO7198457 plus pembrolizumab with an alternative RO7198457 dose, alternative RO7198457 dosing paradigm (e.g., step-up dosing), and/or schedule of administration.

Upon confirmed disease progression (as assessed by the investigator per RECIST v1.1), patients randomized to Arm A will be given the option to cross over and receive combination treatment with RO7198457 and pembrolizumab, provided they meet eligibility criteria described in Section 4.1.3.

The study schema is presented in [Figure 1](#).

Figure 1 Study Schema

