Appendix 3: Schedule of Pharmacokinetic, Immunogenicity, and Biomarker Samples (cont.)

C=cycle;
min=minutes; mos=months;

OT=end of treatment; FU=Follow-Up; hr=hours;

PK=pharmacokinetic; TX DC=treatment discontinuation.

a [REDACTED]

b [REDACTED]

c [REDACTED]

d [REDACTED]

- e Pre-dose pembrolizumab PK collections are to be collected just prior to infusion of pembrolizumab. Post-dose collections are to be collected after infusion of pembrolizumab is completed. On the days that pembrolizumab is given on the same day as RO7198457, post-dose collections are to be collected 30 (± 5) min after infusion of pembrolizumab is completed and before starting infusion of RO7198457 RNA-A.
- f Serum pembrolizumab PK collection will be collected at 2 months post end of treatment *unless pembrolizumab is administered as a new anti-cancer therapy.*
- g At C1D1 (pembrolizumab monotherapy), plasma cytokines sample will be collected prior to pembrolizumab administration and 4–6 hours after infusion of pembrolizumab. For the subsequent cycles, a plasma cytokines sample will only be collected on the days of RO7198457 infusion, regardless of the pembrolizumab cycle and day. Pre-dose sample will be collected prior to infusion of any study drug. Post-dose collections are to be collected 4–6 hours after infusion of RO7198457 RNA-B is completed. NOTE: Pre-and postdose plasma for biomarker cytokines do not need to be drawn if RO7198457 is not available for dosing, except on C1D1.
- h Ad hoc plasma cytokine levels may be drawn once daily in patients experiencing Grade ≥ 2 cytokine release syndrome, infusion-related reaction, or flu-like symptoms.

Appendix 4

Response Evaluation Criteria in Solid Tumors (RECIST v1.1)

Selected sections from the Response Evaluation Criteria in Solid Tumors (RECIST), Version 1.1¹ are presented below, with slight modifications and the addition of explanatory text as needed for clarity.²

MEASURABILITY OF TUMOR AT BASELINE

DEFINITIONS

At baseline, tumor lesions/lymph nodes will be categorized as measurable or non-measurable as follows.

a. Measurable Tumor Lesions

Tumor Lesions. Tumor lesions must be accurately measured in at least one dimension (longest diameter in the plane of measurement is to be recorded) with a minimum size of:

- 10 mm by computed tomography (CT) or magnetic resonance imagining (MRI) scan (CT/MRI scan slice thickness/interval no greater than 5 mm)

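### Grouping safety by treatment received moves Arm B patients who stop or die before their first RO7198457 infusion into the pembrolizumab-alone column, which biases the between-arm comparison of those early events.

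*Combined protocol and SAP*

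**What the plan says.** Four provisions of Section 6.5 matter here.

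- Population: "Safety analyses will be conducted in all randomized patients who received at least one dose of RO7198457 and/or pembrolizumab". An Arm B patient given only pembrolizumab is therefore included.
- Grouping: "Safety analyses will be performed by treatment arm and will be based on actual treatment received".
- Entry to the combination column: "a patient will be included in the RO7198457 plus pembrolizumab arm in the safety analyses if the patient receives any amount of RO7198457", and this applies "regardless of the initial treatment assignment at randomization".
- Counting window: "All adverse events that occur during or after the first study treatment, until 90 days after the final dose of study drug", or until another systemic anti-cancer therapy starts. The clock starts with pembrolizumab at Cycle 1 Day 1, not with RO7198457.

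Section 3.1.1 gives the Arm B sequence as "at least 1 cycle of 200 mg pembrolizumab administered by IV infusion followed by 200 mg pembrolizumab IV Q3W" together with RO7198457. The dosing section is redacted, but Appendix 3, footnote g, says: "For the subsequent cycles, a plasma cytokines sample will only be collected on the days of RO7198457 infusion". In that table the first cytokine sample after Cycle 1 Day 1 falls on Cycle 2 Day 8, and Cycle 2 Day 1 is blank.

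Section 6.4.1 recognises that some patients may never reach the vaccine. It offers an optional landmark PFS analysis, introduced with the words "To account for patients who may discontinue study treatment prior to first administration of RO7198457". Section 6.5 has no counterpart. Under Section 4.6.1, patients who stop treatment are not replaced.

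**The concern.** The combination column can be entered only by patients who remain alive and on study until their first RO7198457 infusion. This is the familiar immortal-time structure. Arm B patients who do not get that far have received pembrolizumab only, and with two columns, grouping by treatment received leaves them under pembrolizumab alone.

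The patients concerned are not a random subset. The first scheduled on-treatment scan is at Week 12 (Section 4.5.5), so stopping before about Day 29 is unlikely to reflect progression on a scheduled scan. Toxicity, death, symptomatic deterioration and withdrawal are the more likely reasons, and most of these belong in safety tables.

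Safety of the combination relative to pembrolizumab alone is a stated objective (Section 2.2), and Section 1.4 anticipates that the combination may bring more frequent or more severe immune-related events. At stake are the rows for adverse events leading to discontinuation and for deaths. In these rows the control column would carry the pre-vaccine events of both arms and the combination column would carry none.

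**Working it through.** **Inputs from the documents.** 120 randomised patients at 2:1 (Sections 3.1.1 and 6.1); a 21-day cycle (Section 3.1.1, dosing schema notes); the grouping rule of Section 6.5; the cytokine schedule and footnote g of Appendix 3.

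**Plan's own figure.** 120 × 2/3 = 80 in Arm B and 120 × 1/3 = 40 in Arm A, which matches the arm sizes in Section 6.1.

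**First RO7198457 day.** Cycle 2 Day 8 = 21 + 8 = Day 29, or Day 27 to 31 with the ±2-day window. The earliest day compatible with at least one full cycle of pembrolizumab alone is Cycle 2 Day 1 = Day 22. A gap of about three to four weeks exists on either reading, and late vaccine would lengthen it.

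**Effect of the rule.** The documents give no early event rate. Assume that a share q of each arm, equal in both, has a treatment-ending or fatal event before first RO7198457, and that all patients are dosed. Then 80q patients move from Arm B to the control column:

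- control column: (40q + 80q) / (40 + 80q)
- combination column: 0 / (80 − 80q)

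| Assumed q, both arms | Control column | Combination column |
|---|---|---|
| 2.5% | 3/42 (7.1%) | 0/78 |
| 5% | 6/44 (13.6%) | 0/76 |
| 10% | 12/48 (25.0%) | 0/72 |
| 15% | 18/52 (34.6%) | 0/68 |

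Grouped as randomised, both arms would show q. The zero follows from the rule and does not depend on q. The control figure simplifies to 3q/(1 + 2q), so for small q it is close to three times the true rate, because the moved events land in the smaller arm.

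**A whole-period row.** Suppose adverse events leading to discontinuation are truly 4/40 (10%) in Arm A and 12/80 (15%) in Arm B, an excess of 5 points. If 4 of the 12 Arm B cases precede first RO7198457, the table shows (4 + 4)/(40 + 4) = 8/44 (18.2%) against (12 − 4)/(80 − 4) = 8/76 (10.5%), a difference of −7.7 points. The sign changes. This is an illustration: it needs one third of Arm B's cases to fall in roughly the first four weeks.

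**The opposite movement.** By the same rule, an Arm A patient who crosses over enters the combination column. If 10 to 20 of the 40 cross over (assumed) and q = 5%, the denominators become 76 + 10 = 86 to 76 + 20 = 96 for the combination, and 44 − 10 = 34 to 44 − 20 = 24 for control.

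**The case against.** The sponsor has several fair answers.

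- *No event that follows RO7198457 leaves the combination column.* True. The difficulty is asymmetry, not attribution. The lead-in counts as time at risk for vaccinated patients, while the treatment-ending events of the lead-in are charged to the other column.
- *Two steps are inferred.* Also true. Section 6.5 says who enters the combination column. Placing never-vaccinated Arm B patients under pembrolizumab alone follows from grouping by treatment received but is not written. Day 29 is reconstructed from a biomarker schedule, and redacted text could allow RO7198457 after pembrolizumab has been stopped.
- *The rates are assumed.* They are. Eligibility requires ECOG 0 or 1 and a life expectancy of at least 12 weeks (Section 4.1.1), which argues against the upper values for deaths.
- *These patients stay visible elsewhere.* PFS and OS are analysed by intention to treat, and Section 6.2 tabulates reasons for stopping treatment. That limits the damage, but it does not give adverse-event incidence by grade and arm.

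Two stronger readings are tempting. A reader might infer that early events in general vanish from the combination column. They do not: lead-in events that do not end treatment are counted there for patients who are later vaccinated, as are treatment-ending events after the first infusion. A reader might also infer that the combination will look safer overall. The documents do not support that, because crossover patients, with their earlier adverse events, move the other way.

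**Conclusion.** The point holds for adverse events that end treatment, and for deaths, before first RO7198457. Under Section 6.5 these are zero in the combination column whatever the true rate, and they are added to a control column half its planned size. At an assumed equal 5% rate the display would be 6/44 (13.6%) against 0/76; over assumed rates of 2.5% to 15% the control figure runs from 7.1% to 34.6%.

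This rests on the implied placement of never-vaccinated Arm B patients and on a lead-in of about four weeks inferred from Appendix 3. The size rests on event rates that the documents do not give. The bias concerns the between-arm comparison of these event types only; no net direction can be claimed for the any-event or serious-event rows. The intention-to-treat PFS and OS analyses are unaffected. The change should be made, but the flaw does not undermine the trial's efficacy conclusions.

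**What to change.** In Section 6.5:

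1. Add comparative tables of adverse events, serious adverse events, adverse events leading to discontinuation, and deaths, by randomised arm, among patients with at least one dose of any study drug. Cut Arm A data at the first crossover dose of RO7198457 and report later events separately. Without that cut, events on crossover treatment, which may last up to 12 months (Section 3.1.4), would be charged to pembrolizumab alone.
2. Keep the as-treated tables as the exposure-based view, and state explicitly where Arm B patients who never receive RO7198457 are placed.
3. Add a supportive table of events from first RO7198457 in Arm B against events from about Day 29 in Arm A patients still on treatment then.

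The cost is a change of wording and one or two extra sets of tables, with no new data, visits or patients. The drawback is that the as-randomised Arm B column includes the lead-in and a few never-vaccinated patients, which slightly dilutes RO7198457-specific rates. The as-treated and supportive tables cover that.
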